10.6 Study Drug Administration

Specific instructions on administration and supplies required for administration are detailed in the Pharmacy Manual. In general, study drug will comprise 1 SC injection administered in the front of the thigh with a 27-gauge needle. Subjects will be observed for at least 1 hour after the SC injection and per the Investigator’s discretion.

10.7 Study Drug Storage

Study drug will be stored by the study sites at 2°C to 8°C under lock at the designated clinic/pharmacy location. Access will be restricted to designated clinic/pharmacy staff. If the temperature of study drug storage in the clinic/pharmacy exceeds or falls below this range, the study drug will be quarantined and the temperature excursion will be reported to the Sponsor or designee. The Sponsor will notify the site if the study drug can be released from quarantine.

10.8 Study Drug Accountability

The study pharmacist/designee is responsible for maintaining accurate and current records accounting for the receipt, dispensing, preparation, use, return (or destruction), and final disposition of all investigational product (IP). All dosage assignments and dispensations will be documented on the source documents. The Master IP Accountability Log should be used to capture receipt, dispensing, and return (or destruction). Electronic IP accountability systems may be used, depending on site preference, as long as the same information is captured. The study monitor will verify entries on these documents throughout the course of the study. Study drug will be labeled with kit numbers but will not reveal whether the kit contains active drug or placebo.

11. Subject Numbering, Stratification, Randomization, and Blinding

11.1 Subject Numbering

Each subject who provides informed consent will be assigned a patient identification number (PID) that uniquely identifies them as a subject in the study. The PID will consist of a 9-digit number:

- The first 3 digits designate the study number. For this study, the number is 218.
- The second 3 digits designate the site number.
- The last 3 digits designate the order of consent at the site (the first subject who provides consent is 001, the second subject is 002, etc.).

The subject will maintain the same PID throughout the study. If a subject signs the ICF but does not meet the inclusion/exclusion criteria or qualifies for the study but does not enroll, the subject may be assigned a new PID and rescreened once. Subjects rescreened within 30 days of signing the initial consent will not need to sign a new ICF providing no changes have been made to the ICF.

11.2 Stratification and Randomization

To be randomized into the study, the subject must have chronic AD (according to the American Academy of Dermatology Consensus Criteria, [Appendix 1](#)) that has been present for at least 3 years before the screening visit. The subject must have an EASI score of ≥ 16 , the subject's AD must involve at least 10% or more of the BSA, along with an IGA score of 3 or above on a scale of 0–4. The subject must also meet all other applicable inclusion criteria and none of the exclusion criteria.

If the subject qualifies for the study after completing all of the screening procedures, on the day of the first SC injection (Dosing Day 1), the site will access the IRT system in order to stratify and randomize the subject in the study. The IRT system will then randomly assign the subject at an allocation ratio to lirentelimab SC 300 mg, or placebo SC for 7 doses in a double-blind manner and will send an email to the pharmacist and/or designee detailing the kit number(s) to use to prepare the SC injection.

The subject will be stratified based on:

- 1) Biologic-naïve status vs. biologic-exposed status
- 2) IGA score at baseline: IGA score of 3 vs IGA score of 4

Approximately 130 subjects (65 per arm) will be randomized to treatment with lirentelimab SC or placebo SC. A subject is considered enrolled in the study when the subject receives the first dose of study drug. For subsequent SC injections the coordinator will access the IRT system on the day of SC injection and enter the PID; the system will assign the subject the dose according to the subject's randomization number. The pharmacist and/or designee will then receive an email detailing the kit number(s) to prepare.

Prior to each SC injection, the Investigator or designee will confirm the PID recorded on the SC syringe provided by the pharmacist matches the subject. The patient identification should be confirmed and documented by a second party prior to administering the SC injection(s), whenever possible. There will not be any unblinding information on the IRT notification to the pharmacist or on the vials provided to the site.

The assignment of treatment to lirentelimab SC or placebo SC will be securely retained in the IRT system until such time as designated by the Statistical Analysis Plan (SAP).

11.3 Blinding

The identity of test and control treatments will not be known to Investigators, Sponsor, research staff, subjects, or the study monitor. The following study procedures will be in place to ensure double-blind administration of study treatments:

- Access to the randomization codes will be strictly controlled by the IRT system.
- Throughout the double-blind study, the blind should remain unbroken except for an emergency when knowledge of the subject's study medication is necessary for further management or if required for regulatory reporting. The Allakos Medical Monitor approves any emergency blind break, if at all possible, prior to the unblinding.

- The lirentelimab and placebo for SC injection will be identical in appearance.
- Results from the analysis of blood samples for PK and ADA will not be provided to the Investigator and Sponsor until after final database lock of the double-blind study.
- Results from the analysis of blood samples for histamine/tryptase tests (collected in case of possible anaphylaxis) will not be provided to the Investigator and Sponsor until after final database lock of the double-blind study, unless required for immediate safety reasons.
- Results of the assessments noted below will not be provided to the Investigator and Sponsor until after final database lock of the double-blind study, so as to not introduce bias. The results will be reviewed on an ongoing basis by the Safety Monitor and escalated as appropriate.
 - Differential cell counts including neutrophils, eosinophils, basophils, monocytes, and lymphocytes.

Other than under the conditions described above, the study blind will be revealed on completion of the study as noted in Section [17.4](#).

11.4 Breaking the Blind

Breaking the blind in a clinical study on an emergency basis by the site should only occur when knowledge of the treatment to which a subject was allocated would have implications for the emergency medical management of the subject, if required for regulatory reporting, or if there is a pregnancy during the pregnancy reporting period.

If necessary, emergency breaking of the blind can be conducted through the IRT by the Investigator or other registered site users and/or the Medical Monitor. Whenever possible, the Investigator should contact the Medical Monitor before an emergency breaking of the blind. Reason for unblinding, person conducting the unblinding, personnel who know the unblinded treatment, and date/time of unblinding will be recorded.

12. Study Procedures and Guidelines

[Table 1](#) provides the schedule of assessments depicting the required testing procedures to be performed for the duration of the study. When multiple evaluations are scheduled at the same time point, the priority for each will be as follows:

- At home: For the daily questionnaires that the subject completes at home, the subject should complete the [REDACTED] except on days of study visits when the [REDACTED] will be completed while the subject is at the study site.

- At the clinic:
 - 1) [REDACTED] IGA, EASI, [REDACTED], and Atopic Conditions Questionnaire.
 - 2) Vital signs will be obtained after the subject has been at rest for ≥ 5 minutes.
 - 3) Physical examinations can be performed and urine samples can be collected either before or after other evaluations, unless otherwise specified.

12.1 Pharmacodynamic/Efficacy-Related Procedures

To ensure consistency in grading, the same Investigator should make all assessments for a subject starting from screening and continuing throughout the double-blind period and OLE period of the study whenever possible. It will not be considered a protocol deviation if a different Investigator makes an assessment for a subject during the study, but this should be avoided as much as possible.

12.1.1 Validated Investigator Global Assessment

The validated Investigator Global Assessment (vIGA) is a 5-point scale that provides a global clinical assessment of AD severity ranging from 0 to 4 and assesses disease severity and clinical response using a 5-point scale: 0 = clear; 1 = almost clear; 2 = mild; 3 = moderate; and 4 = severe ([Appendix 2](#)). The score is determined by ranking the extent of erythema and papulation/infiltration. A decrease in score relates to an improvement in signs and symptoms. The vIGA is a physician-conducted assessment.

The vIGA will be determined during screening, and a baseline will be established. A vIGA score of ≥ 3 is required to enroll in the study. The vIGA will be measured by Investigators during screening, predose on all dosing days, and during each follow-up day or ET.

12.1.2 Eczema Area and Severity Index

During screening, the EASI will be determined, and a baseline will be established. The EASI score is a tool used to measure the extent (area) and severity of atopic eczema with respect to erythema, excoriation, infiltration, and lichenification at 4 anatomic sites of the body: lower and upper extremities, trunk, and head ([Appendix 3](#)). The total EASI score will be in a range from 0 to 72 points (from no disease to maximum disease severity) and is conducted by the Investigator. An EASI score of > 16 during screening is required to enroll in the study. The EASI will be determined by Investigators during screening, predose on all dosing days, and during all follow-up on Days 99, 141, and 169 or ET.

Enrollment will be monitored to limit the impact of randomizing a disproportionately large number of subjects with an EASI score in the lower range, reflecting more moderate disease only (i.e., EASI score < 22). This will also provide a subject population with a full range of EASI scores consistent with the intent to study lirentelimab in moderate-to-severe AD disease.

12.1.3 [REDACTED]

The [REDACTED] is a validated [REDACTED] patient-reported outcome (PRO) of [REDACTED] [REDACTED] that will be completed by the subject on a daily basis, at approximately the same time every day (Appendix 4). On dosing days, [REDACTED] should be completed while subject is at the site.

During screening, [REDACTED] will be determined, and a baseline will be established. The [REDACTED] rating system captures the [REDACTED]. The following question will be presented to subjects:

Scale of [REDACTED]

12.1.4 [REDACTED]

The [REDACTED] is a simple measurement of the [REDACTED] (Appendix 5). At screening, the Investigator will determine the [REDACTED] [REDACTED]. The subject is required to have [REDACTED] to enroll in the study. The [REDACTED] will be determined by the Investigator during screening, predose on all dosing days, and during follow-up on Days 99, 141, and 169 or ET.

12.1.5 [REDACTED]

The [REDACTED] is a clinical tool used to determine the [REDACTED]. The [REDACTED] tool was developed by the [REDACTED] as a measure of [REDACTED]. It includes assessment of the [REDACTED] by the Investigator in addition to patient-reported symptoms. Total score ranges from [REDACTED] [REDACTED]. During screening, [REDACTED] will be determined, and a baseline will be established. In addition, [REDACTED] will also be determined predose on all dosing days and during follow-up on Days 99, 141, and 169 or ET.

12.1.6 [REDACTED]

The [REDACTED] is a [REDACTED] questionnaire used to measure [REDACTED] [REDACTED] of an affected person (Appendix 6). The format is a simple response [REDACTED] [REDACTED] that assess [REDACTED] over the past week with an

overall scoring system of [REDACTED]; a high score is indicative of a [REDACTED] is a self-administered questionnaire. Subjects will complete this during screening, predose on all dosing days, and during follow-up on Days 99, 141, and 169 or ET.

12.1.7 Atopic Conditions Questionnaire

On Day 1, Day 99 and OLE Day 99, subjects will be prompted to answer additional questions about severity of symptoms related to asthma, allergic rhinitis and allergic conjunctivitis (Appendix 7).

12.1.8 Photographs

The site staff may take photographs of subjects' AD disease to track study drug response and disease progression. This will depend on the sites' standard operating procedures regarding photography. Subjects will be consented before the Sponsor will have access to any images.

12.1.9 Complete Blood Count with Differential

Blood for complete blood count (CBC) with differential, including absolute blood eosinophil count, will be obtained at screening, just prior to each SC injection, 1 hour (± 15 minutes) after the end of each SC injection, and on Days 99, 141, and 169 (± 5) or 14, 56, and 84 (± 5) days after last dose if ET. The blood sample will be processed and shipped in accordance with the Laboratory Manual and lab kit instructions. A central laboratory will analyze the blood sample and provide results for CBC with differential including hemoglobin, hematocrit, platelet count, red blood cell count, white blood cell count, and absolute differential count (neutrophils, lymphocytes, monocytes, eosinophils, and basophils).

During the double-blind period, all differential blood counts from Day 1 (post-dose) through the end of the subject's participation will be blinded to the Sponsor and the site. An unscheduled CBC may be collected at the request of the Safety Monitor. The blood differential test results (neutrophils, eosinophils, basophils, monocytes, and lymphocytes) will be blinded from the Investigator and Sponsor from post-dose Day 1 through Day 169 or ET and until database lock has occurred. If a subject continues to the OLE period of the study, all differential blood counts will be blinded for the first (OLE Day 1) predose assessments and will be unblinded after the subject has received the first dose of the study drug.

As described in the Investigator's Brochure, changes in certain lab results are a part of the expected effects of lirentelimab and could potentially introduce bias in blinded members of the study. The Safety Monitor will have real-time access to these laboratory results and will review and escalate any concerns/issues to the Medical Monitor and/or the site as appropriate. An

unscheduled CBC with differential may be collected if requested by the Safety Monitor. All panic alerts for blinded values will be sent to the Safety Monitor and evaluated in real time.

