2.3 Overview of Clinical Studies

Lirentelimab IV, administered every 4 weeks, has been previously tested in over 700 healthy volunteers and patients with indolent systemic mastocytosis (ISM), chronic urticaria (CU), severe allergic conjunctivitis (AC), mast cell gastritis, and eosinophilic gastritis (EG) and/or eosinophilic duodenitis (EoD). Multiple doses of 3 mg/kg have been given to patients with ISM, CU, AC, mast cell gastritis, and EG and/or EoD.

In general, lirentelimab IV has been well tolerated. The most common treatment-emergent adverse events (TEAE) observed were infusion-related reactions (IRR). The IRR were mostly mild to moderate, and occurred most often during the first infusion. IRR that were deemed more serious typically resolved within 24 hours, and additional corticosteroids and/or antihistamines were used in cases when slowing the rate of infusion and additional supportive care alone did not resolve the issue. Common symptoms of IRR were headache, nausea, sweating, flushing, and redness. Most IRR that occurred during the infusion could be managed by slowing or temporary interruption of the infusion, with minimal intervention. In subjects with ISM, CU, severe AC, and EG/EoD, fewer adverse events (AE) including IRR were reported during the second and subsequent infusions when compared to the first infusion. The risk of IRR has been substantially reduced by administration of a single dose of oral corticosteroid (e.g., prednisone 60 mg) given orally 12 to 24 hours prior to the first dose of lirentelimab IV.

Study AK002-017 evaluated the PK and PD of lirentelimab IV and SC in healthy volunteers. Subjects received 0.3, 1, 3, or 5 mg/kg or a fixed dose of 300 mg or 450 mg lirentelimab SC, or 1 mg/kg or 3 mg/kg lirentelimab IV.

In each of the SC cohorts, 8 subjects were randomized to lirentelimab (6 per group) or placebo (2 per group) in a double-blind manner; 12 subjects received lirentelimab IV (6 subjects per group) in an open-label manner.

The study showed that the PD effect (depletion of blood eosinophils) occurred within 1 hour of dosing and lasted for at least 1 month at IV and SC doses of 1 mg/kg and for 3 months at all higher IV and SC doses. The SC injections were well tolerated, and no injection site reactions or general injection reactions were noted at any dose demonstrating suitability for further evaluation.

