- 14) Blood for CBC with differential, including absolute blood eosinophil count, will be obtained at screening, just prior to each SC injection, 1 hour (± 15 minutes) after the end of each SC injection, and on all follow-up days (14, 56, and 84 [± 5] days after last dose if ET). All differential blood counts from Day 1 (post-dose) through the end of the subject's participation in the double-blind period will be blinded to the Sponsor and the site. An unscheduled CBC may be collected at the request of the Safety Monitor.
- 15) Blood for PK will be obtained predose on all dosing days as well as on Day 8 (± 3) and on follow-up days (14, 56 and 84 [± 5] days after last dose of study drug if ET).
- 16) Blood for ADA will be collected predose on dosing Days 1, 43, and 85 (± 5), as well as on Day 8 (± 3), and on follow-up Days 99 and 169 (14 and 84 [± 5] days after last dose of study drug if ET). The ADA sample will also be collected any time an immunogenicity-related AE occurs.
- 17) Urine will be collected for dipstick pregnancy test on all dosing days, Day 8, and all follow-up days (14, 56, and 84 days after last dose of study drug if ET) for all subjects of childbearing potential. Test kits will be supplied by the central laboratory. Tests will be completed on site and evaluated prior to each SC injection.
- 18) Urine for standard urinalysis will be obtained at screening and on follow-up Days 99 and 169 (14 and 84 days [± 5] if ET), and symptom-based, as necessary.
- 19) Randomization will be conducted through the IRT system. Subjects will be randomized 1:1, lirentelimab SC 300 mg or placebo SC. They will be stratified based on biologic status and IGA score at baseline.
- 20) The capture of non-serious AE and adverse events of special interest (AESI) will begin after the first dose of study drug has occurred.

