12.3 Clinical Laboratory Measurements

Blood and urine samples for clinical safety laboratory tests will be collected at the time points described below. Investigators may have additional laboratory tests performed for the purpose of planning treatment administration or following AE or abnormal laboratory values.

The site will process and ship blood and urine samples per central laboratory instructions. A central laboratory or designee will analyze blood and urine samples and provide results for the clinical safety laboratory tests.

Clinical laboratory testing may be performed locally, if necessary, with prior approval from Allakos. The site will strive to use the central laboratory whenever possible.

For any laboratory test value outside the reference range, the Investigator will determine clinical significance: Not Clinically Significant (NCS) or Clinically Significant (CS). An abnormal laboratory value should be deemed CS if any of the following conditions are met:

- The abnormality suggests a disease and/or organ toxicity that is new or has worsened from baseline.
- The abnormality is of a degree that requires additional active management, e.g., change of study drug dose, discontinuation of the study drug, close observation, more frequent follow-up assessments, or further diagnostic investigation.

Therefore, a clinically significant laboratory value is a lab test value that indicates a new disease process, an exacerbation or worsening of an existing condition, or requires further action to be taken.

For any laboratory test value outside the reference range that the Investigator considers clinically significant, the Investigator will:

- Repeat the test to verify the out-of-range value.
- Follow the out-of-range value to a satisfactory clinical resolution.
- Record as an AE any laboratory test value after start of study drug that:
 - The Investigator considers clinically significant.
 - Requires a subject to be discontinued from the study.
 - Requires a subject to receive treatment.

Blood will be obtained for CBC with differential as described in Section 12.1.9.

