20.11 Appendix 11: Open Label Extension Period (Optional)

20.11.1 Summary of the Open-Label Extended Dosing Period

Subjects who complete the double-blind, placebo-controlled treatment period (including the Day 99 study visit) and meet the open-label extended dosing eligibility criteria will be given the option to receive 7 doses of 300 mg lirentelimab SC through the open-label extended (OLE) dosing period.

On Day 99 (± 5 days) of the double-blind period, eligible subjects participating in the OLE period will begin following the OLE Schedule of Events ([Table 8](#)) and will no longer follow the double-blind period Schedule of Events ([Table 1](#)). If OLE Day 1 is completed on the same day as Day 99, already completed assessments (for Day 99) do not need to be repeated (for OLE Day 1), as long as they are performed within time frames noted in the [Table 8](#) notes.

The OLE dosing period is summarized as follows:

- The Investigator will evaluate whether the subject is eligible for OLE. If eligible, the subject will be given the option to participate in the OLE period and receive 7 doses of open-label 300 mg lirentelimab SC administered every 2 weeks starting on Day 99 of the double-blind period, which will be considered Day 1 of the OLE period. OLE dosing may be delayed for up to 7 days after completion of the Day 99 visit.
- On Day 99, after completing all Day 99 assessments, eligible subjects who choose to participate in the OLE period will begin following the OLE Schedule of Events ([Table 8](#)).
- Day 1 of the OLE can occur up to 7 days following Day 99 of the double-blind period. In case Day 1 of the OLE is not the same as Day 99 of the double-blind period, applicable subjects (women of childbearing potential) will have a urine dipstick pregnancy test.
- After OLE Day 1, subsequent doses will be given on OLE Days 15, 29, 43, 57, 71, and 85 (± 5 days).
- All differential blood counts will be blinded to the Sponsor and the site until after OLE Day 1 dosing.
- Subjects will remain at the site for at least 1 hour of observation after each dose. In the event of an IRR, the subject may require prolonged observation (>1 hour or until the symptoms resolve), as per Investigator discretion.
- Subjects will be followed for approximately 12 weeks after the last dose. Follow-up visits will occur on OLE Days 99, 141, and 169 (14, 56, and 84 [± 5] days) following the last dose of open-label study drug.

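### Post-dose total white cell count is on no list of masked results, so it may partly reveal the arm to the investigator who scores EASI and vIGA, mainly in subjects with high baseline eosinophils

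*Protocol*

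**What the plan says.** **What is masked.** Protocol 12.1.9: "The blood differential test results (neutrophils, eosinophils, basophils, monocytes, and lymphocytes) will be blinded from the Investigator and Sponsor", from Day 1 post-dose until database lock. Protocol 11.3 lists the same items: "Differential cell counts including neutrophils, eosinophils, basophils, monocytes, and lymphocytes". Protocol 4.4, 8.6 and Table 1 note 14, and note 14 of the SAP's schedule, also mask differential or cell counts only (8.6 adds tissue eosinophil and mast cell counts).

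**What is reported.** Under 12.1.9 the central laboratory will "provide results for CBC with differential including hemoglobin, hematocrit, platelet count, red blood cell count, white blood cell count, and absolute differential count". WBC is therefore a result separate from the differential. It is drawn at screening, before and 1 hour after every dose, and at follow-up. Under 12.3, "For any laboratory test value outside the reference range, the Investigator will determine clinical significance", which implies that unmasked results reach the site.

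**Drug effect.** Protocol 2.3: "the PD effect (depletion of blood eosinophils) occurred within 1 hour of dosing", lasting at least 1 month at 1 mg/kg and 3 months at higher doses.

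**Who scores.** The investigator scores vIGA (12.1.1) and EASI (12.1.2), preferably the same person throughout (12.1), and decides on rescue (9.3). Rescue counts as non-response (16.6.1; SAP 6.9.1).

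**Extension.** Protocol 20.11.1: "All differential blood counts will be blinded to the Sponsor and the site until after OLE Day 1 dosing". Section 12.1.9 likewise says the counts are unblinded once the first OLE dose has been given. Section 11.3 holds differentials until final lock of the double-blind study.

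**The concern.** Masking five components while leaving their total open protects less than intended. The site knows the starting eosinophil count, because masking begins only after the first dose, and so knows roughly what fall to look for. Section 12.1.9 itself accepts that expected laboratory changes could bias blinded staff.

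The primary endpoint (EASI-75) and both secondary endpoints (percent change in EASI; IGA 0 or 1 with a 2-point improvement) rest on that investigator's scores. No assessor without laboratory access is described. A partial guess could affect scoring and rescue decisions alike.

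The OLE wording raises a different risk. Read literally, it shows site and sponsor a subject's double-blind differentials while other subjects are still on treatment. It also does so before the blinded intercurrent-event adjudication (SAP 4.2.5) and the population decisions (Protocol 17.4, SAP 5.6) are complete.

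**Working it through.** **1. The plan's own figures.** The documents give no baseline eosinophil distribution, no WBC variability and no estimate of unblinding. The design figures used in step 5 are the 15% placebo response and 65 per arm (Protocol 16.1). The stated 55 per arm for 44% vs 15% is reproduced: 57 with continuity correction, and exact Fisher power of 89.8% at 55. The masking point does not depend on it.

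**2. Which samples carry the signal.** Depletion outlasts the 2-week dosing interval, so in the drug arm only the Dose 1 pair shows the acute fall. Values available before Week 14 scoring are 1 post-dose value on Day 1 plus 2 at each of 6 later doses, 1 + 12 = 13. They are compared with 2 open baseline values (screening and Day 1 predose).

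**3. Accuracy of guessing the arm.** Assumptions not in the documents: mean WBC 7.0 x10^9/L; within-person CV of 5% to 15%, so SD = 0.35 to 1.05; the WBC fall equals the baseline eosinophil count E. With the cut at E/2:

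- Dose 1 pair: Phi[(E/2) / (SD x sqrt 2)]
- Serial values: Phi[(E/2) / (SD x sqrt(1/2 + 1/13))]

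| E (x10^9/L) | Dose 1 pair | Serial values |
|---|---|---|
| 0.2 | 52.7–58.0% | 55.0–64.7% |
| 0.5 | 56.7–69.3% | 62.3–82.6% |
| 1.0 | 63.2–84.4% | 73.5–97.0% |
| 1.5 | 69.3–93.5% | 82.6–99.8% |

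Chance is 50%. Example: E = 1.5 and CV 5% give 0.75 / (0.35 x 1.414) = 1.515, and Phi = 0.935.

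**4. Second model for the Dose 1 pair.** Assume that the SD s of the 1-hour change is 0.4 to 0.8 x10^9/L, and use AUC = Phi[E / (s x sqrt 2)]. This gives 0.57–0.64 at E = 0.2, 0.64–0.76 at 0.4, 0.76–0.92 at 0.8 and 0.91–1.00 at 1.5. The pattern is the same.

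**5. What a scoring drift would do.** This is an illustration, not a prediction. With a true rate of 15% in both arms, 65 per arm and two-sided alpha of 0.05 (SAP 5.8), suppose guessing raises the scored response in the active arm by b. The rejection probability is Phi[(b − 1.96 s0)/s1] + Phi[(−b − 1.96 s0)/s1], where s0 and s1 are the pooled and unpooled standard errors. It is 5.0% at b = 0, 7.4% at 3 points, 11.6% at 5 points and 29.5% at 10 points. At 5 points, s0 = 0.0667 and s1 = 0.0665.

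**6. OLE text side by side.** Section 11.3, and the sentence in 12.1.9 that masks through Day 169 or early termination and until lock, keep differentials closed. Section 20.11.1 and the last sentence of the same 12.1.9 paragraph open them after the first OLE dose, without restricting this to later samples. Section 17.4 releases the code to sponsor analysts after a provisional Day 99 lock. SAP 5.6 describes a single lock after all subjects finish the double-blind period. These rules give different release points.

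**The case against.** **WBC visibility.** A reader might infer that sites are known to receive post-dose WBC. No passage says so. Visibility is inferred from WBC's absence from every masking list and from the 12.3 review duty. The Laboratory Manual, which is not available here, might mask it. This stands as a limit on certainty. If WBC is already masked, a protocol statement settles the point.

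**Inferring the arm in general.** A reader might also infer that the assessor can work out the arm for subjects generally. The figures do not support this. At 0.2 x10^9/L the fall is lost in ordinary variation. There is no eosinophil entry minimum, and 2.4 says only that eosinophils may be elevated. Section 14.11 shows that subjects above 1500/µL can enter, not how many do. The OLE rule about lymphocyte recovery hints at an additional fall but gives no size or timing.

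**Seven separate signals.** The pre/post sampling at all 7 doses might be read as 7 independent signals. It is not, for the reason in step 2.

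**Practical limits.** EASI and vIGA are completed predose, samples are read centrally and each site expects about two subjects. Same-visit results are therefore unlikely to be in hand at scoring, and an investigator has little experience for calibrating WBC changes. These limits reduce the leak. They do not remove it, because results from earlier visits remain available.

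**OLE release.** It might be thought to bias the released subject's own Week 14 scores. It cannot, because OLE dosing follows completion of the Day 99 assessments. OLE entrants have also had all 7 injections (20.11.4), so few discontinuations remain to adjudicate. What remains exposed is adjudication of prohibited and rescue medication, and the population decisions.

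**Conclusion.** The gap holds as a partial unblinding route. Total WBC is not listed as masked, and the person who may see it determines the primary and both secondary endpoints. Discrimination runs from near chance at about 0.2 x10^9/L to strong at about 1.5 x10^9/L. This rests on assumed WBC variability and a fall equal to the baseline eosinophil count, neither of which the documents give. The share of subjects with high counts is unknown, so no trial-level bias can be stated. Step 5 shows only how the false-positive rate would respond to a given drift. The OLE wording is a separate internal conflict that must be reconciled. The point merits a change because the sponsor recognises this kind of bias and the change is small. Confidence is medium.

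**What to change.** **Masking.** Add post-dose total WBC to the results withheld from site and sponsor and routed to the Safety Monitor, in Protocol 4.4, 8.6, 11.3, 12.1.9 and Table 1 note 14, and in the matching SAP note. Make the out-of-range review in 12.3 consistent with this, and state how masking applies to the local testing that 12.3 permits. If the Laboratory Manual already masks WBC, say so in these places.

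**Extension.** In 12.1.9 and 20.11.1, limit unblinding to samples drawn after the first OLE dose. Keep double-blind samples, including Day 99 and OLE Day 1 predose, masked at least until intercurrent-event adjudication and population decisions are complete and the database is locked. Reconcile 11.3 with the provisional-lock code release in 17.4 and the single lock in SAP 5.6.

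**Cost.** A central-laboratory reporting change and consistent edits to the sections named. Sample size, power and endpoints are unchanged. Investigators lose routine post-dose total WBC. Neutrophils are already withheld, and the Safety Monitor already has real-time access to the masked results, receives panic alerts for them and escalates concerns.
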